4.1. Study Population

Subjects will be screened to confirm eligibility requirements for participation using the VRC 500 screening protocol. The screening and education process required prior to enrollment is designed to ensure that subjects comprehend the purpose, details and risks/benefits of the study. All inclusion and exclusion criteria must be met for eligibility.

4.1.1. Inclusion Criteria

A subject must meet all of the following criteria:

1. Willing and able to complete the informed consent process.
2. Able to provide proof of identity to the satisfaction of the study clinician completing the enrollment process.
3. Available for clinical follow-up through the last study visit.
4. 18 to 60 years of age.
5. In good general health without clinically significant medical history.

6. Physical examination without clinically significant findings within the 56 days prior to enrollment.
7. Adequate venous access if assigned to an IV group or adequate abdominal subcutaneous tissue if assigned to SC group.
8. Willing to have blood samples collected, stored indefinitely, and used for research purposes.

Laboratory Criteria within 56 days prior to enrollment:

9. White blood cell count (WBC): 2,500-12,000/mm³.
10. WBC differential either within institutional normal range or accompanied by the Principal Investigator (PI) or designee approval.
11. Platelets: 125,000 – 500,000/mm³.
12. Hemoglobin within institutional normal range or accompanied by PI or designee approval.
13. Creatinine: \leq 1.1 x Upper Limit of Normal (ULN).
14. ALT: \leq 1.25 x ULN.
15. AST: \leq 1.25 x ULN.
16. Negative for HIV infection by an FDA approved method of detection.

Female-Specific Criteria:

17. Agrees to use an effective means of birth control from 21 days prior to enrollment through the duration of study participation.
18. Negative β -HCG (human chorionic gonadotropin) pregnancy test (urine or serum) on day of enrollment for women presumed to be of reproductive potential.

4.1.2. Exclusion Criteria***A subject will be excluded if one or more of the following conditions apply:***

1. Woman who is breast-feeding or planning to become pregnant during study participation.
2. Weight $>$ 115 kg.
3. Any history of a severe allergic reaction with generalized urticaria, angioedema or anaphylaxis prior to enrollment that has a reasonable risk of recurrence during the study.
4. Hypertension that is not well controlled.
5. Receipt of any investigational study product within 28 days prior to enrollment (Note: Emergency Use Authorization of a COVID-19 vaccine is not exclusionary).
6. Receipt of an investigational HIV vaccine or anti-HIV monoclonal antibody.
7. Receipt of any live attenuated vaccine within 28 days prior to enrollment.
8. Receipt of any vaccine within 2 weeks prior to enrollment.

9. Bleeding disorder diagnosed by a doctor (e.g., factor deficiency, coagulopathy, or platelet disorder requiring special precautions) or significant bruising or bleeding difficulties with IM injections or blood draws.
10. Any other chronic or clinically significant medical condition that in the opinion of the investigator would jeopardize the safety or rights of the volunteer, including but not limited to: diabetes mellitus type I, chronic hepatitis; OR clinically significant forms of: drug or alcohol abuse, asthma, infectious disease, autoimmune disease, psychiatric disorder, heart disease, or cancer.

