4.2. Inclusion of Vulnerable Subjects

4.2.1. Pregnant Women

This is a first-in-human trial in healthy subjects, ≥ 18 years of age. Because the effects of the vaccine on the fetus are not known, pregnant women will not be eligible for the trial. Women of childbearing potential must utilize a highly effective method of contraception and will be required to have a negative urine or serum pregnancy test within 24 hours prior to each product administration.

Pregnancy, if it occurs during study participation, will be recorded in the study database. These participants will not continue to receive any further study product administrations, **Error!**

Reference source not found. research sample collections, or research procedures. Pregnant participants will continue to be followed for clinical safety and to collect the pregnancy outcome. Any follow-up procedures and/or data collected will be for clinical/safety outcome purposes only. Pregnancy will be reported as described in Section 5.6.

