4.3.2. Screening

All screening procedures for this study are described and will be completed through the Vaccine Research Center's screening protocol, VRC 500 (NIH 11-I-0164) used for all VRC IND studies conducted at the NIH Clinical Center. The Recruitment Plan per NIH Policy 302 for all VRC studies can be found in the NIH IRB approved VRC 500 protocol. Subjects will be recruited through Institutional Review Board (IRB)-approved advertising. Screening evaluations performed to determine eligibility for study participation will include medical history review, physical exam, and the clinical laboratory tests as detailed in the Schedule of Evaluations, [Appendix I](#)). No screening procedures will be done under protocol VRC 615.

Additional assessments of health may be conducted at screening based on clinical judgment. Screening evaluations for specific eligibility criteria must be completed within the time interval specified prior to enrollment for the given parameter and may be repeated, as needed, to confirm eligibility.

Blood samples for research can be drawn at any time during the screening period and are not subject to a time interval. Informed consent documents will be reviewed. Counseling related to potential risks of the study product, pregnancy prevention, and HIV risk-reduction will be performed. An Assessment of Understanding (AoU) will be completed in association with enrollment into VRC 615. Screening records will be maintained to document the reason why an individual was screened but not enrolled.

Subjects who are not up to date on standard vaccinations may receive these, if available, during their participation in the screening protocol or at a later date during study participation as described in [Sections 4.3.4](#) and [4.3.9](#).

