¹Day 0=day of first product administration. Day 0 is preferably scheduled within 14 days after enrollment but may be scheduled up to 42 days after enrollment to allow for the possibility of study pauses or scheduling difficulty with the approval of the PI. Day 0 evaluations prior to product administration are the baseline for assessing subsequent AEs.

(Footnotes continue to next page)

² Screening includes physical exam with vital signs (blood pressure, temperature, pulse, respiratory rate), height and weight. At other visits, if medically indicated, perform a targeted exam. Otherwise only vital signs are required, except at Visit 02 when the current weight is also obtained to use for ordering the study product, dosed based on “mg/kg.”

³ The PK blood draw “visits,” defined by hours after an infusion, are relative to the exact time of the end of infusion (EOI). The exact start and end times of product administration and the time of PK blood draw(s) are recorded to ensure accurate PK analysis. In all IV groups, subjects will be observed in clinic for at least 2 hours following completion of product administration.

⁴ Pregnancy test results must be negative for women of reproductive potential before each product administration. Complete a Pregnancy Prevention Form when pregnancy test is given.

Schedule 2: SC Group 2 (5 mg/kg)																
Visit Number	01	01R	02	02A	02E	02F	02G	03	04	05	06	07	08	11	12	13
Time After Infusion			Pre	EOI	24hr	48hr	72hr	Wk1	Wk2	Wk3	Wk4	Wk8	Wk12	Wk16	Wk20	Wk24
¹ Day of Study	-56 to -1	-42 to 0	D0	D0	D1	D2	D3	D7	D14	D21	D28	D56	D84	D112	D140	D168
Clinical	Tube*	Screen	Enroll	Day of Injection												
VRC 500 Screening Consent		X														
VRC 615 AoU; Consent			X													
² Physical examination		X	X	X	X	X	X	X	X	X	X	X	X	X	X	X
Complete medical history at screen; then interim med hx		X	X	X		X	X	X	X	X	X	X	X	X	X	X
³ VRC01.23LS Administration				X												
Begin 7-day Diary Card				X												
CBC / differential	EDTA	3		3		3			3	3		3		3		
ALT, creatinine	GLT	4		4		4			4	4		4		4		
CMP: Total bili, BUN, albumin, protein, calcium, Na, K, Cl, CO ₂ , glucose, AST, ALP	GLT	X		X						X						
⁴ Pregnancy test: urine or serum		X	X	X						X				X		X
⁴ Pregnancy Prevention Counseling		X	X	X						X				X		X
HIV Ab/Ag combo test	EDTA	3							3							
HIV Risk-Reduction Counseling		X		X					X							
Research Samples																
PK	SST			4		4	4	4	4	4	4	4	4	4	4	4
PBMCs	EDTA			20		20										
Serum	SST			24			8	8	8	8	8	8	8	8	8	8

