- Subjects who receive only one product administration will follow Schedule 4 through Visit 07, and then move to Schedule 5.
- Subjects who receive two product administrations will follow Schedule 4 through Visit 12 and then move to Schedule 5.

Schedule 4 (continued): IV Group 6 (20 mg/kg by repeat dosing)											
Visit Number*		13E	13F	14	15	16	17	18	19	20	21
Time After Infusion		24hr	48hr	Wk25	Wk26	Wk28	Wk32	Wk36	Wk40	Wk44	Wk48
Day of Study		D169	D170	D175	D182	D196	D224	D252	D280	D308	D336
Clinical	Tube										
Physical examination if medically indicated, otherwise only vitals			X	X	X	X	X	X	X	X	X
Interim medical history			X	X	X	X	X	X	X	X	X
Phone contact; clinic visit if indicated		X									
CBC / differential	EDTA		3	3	3	3					
ALT, creatinine	GLT		4	4	4	4					
CMP: Total bili, BUN, albumin, protein, calcium, Na, K, Cl, CO2, glucose, AST, ALP	GLT				X						
Pregnancy Test: urine or serum					X			X			X
Pregnancy Prevention Counseling when pregnancy test given					X			X			X
HIV Ab/Ag combo test	EDTA			3							
HIV Risk-Reduction Counseling				X							
Research Samples											
PK	SST		4	4	4	4	4	4	4	4	4
Serum	SST		8	8	8	8	8	8	8	8	8
Daily Volume (mL)		0	19	22	19	19	12	12	12	12	12
Cumulative Volume (mL)		341	360	382	401	420	432	444	456	468	480

Visit windows: Schedule visits 13E through 21 with respect to visit 13.

Visit 13E (+1 day); Visit 13F (+2 days), Visits 14-17 (± 2 days), and Visits 18-21 (± 7 days).

* The study schedule study schedule for subjects who discontinue product administration will be modified as follows:

- Subjects who receive only one product administration will follow Schedule 4 through Visit 7, and then move to Schedule 5.
- Subjects who receive two product administrations will follow Schedule 4 through Visit 12 and then move to Schedule 5.

Schedule 5: For Subjects in Groups 5 and 6 Discontinued from Further Product Administration(s)									
		Visit Number	08	11	12	13	16	17	18
		Time After Infusion	Wk12	Wk16	Wk20	Wk24	Wk28	Wk32	Wk36
		Day of Study	D84	D112	D140	D168	D196	D224	D252
Clinical	Tube*								
Physical examination if medically indicated, otherwise only vitals			X	X	X	X	X	X	X
Interim medical history			X	X	X	X	X	X	X
Pregnancy Test: urine or serum				X		X			X
Pregnancy Prevention Counseling when pregnancy test given				X		X			X
Research Samples									
PK	SST	4	4	4	4	4	4	4	4
Serum	SST	8	8	8	8	8	8	8	8
Daily Volume (mL)			12	12	12	12	12	12	12
If starting at Visit 8	Cumulative Volume (mL), Group 5		211	223	235	247			

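### Inclusion criterion 17 sets a weaker contraception standard than section 4.2.1, and sets it for all women rather than for women of childbearing potential

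*Combined protocol and SAP*

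**What the plan says.** Criterion 17 stands in section 4.1.1 under the female-specific heading: "Agrees to use an effective means of birth control from 21 days prior to enrollment through the duration of study participation". It has no qualifier for childbearing potential. Criterion 18, the next item, has one: its pregnancy test is required "on day of enrollment for women presumed to be of reproductive potential".

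Section 4.2.1 gives the reason for caution: "Because the effects of the vaccine on the fetus are not known, pregnant women will not be eligible for the trial". It then sets its own rule: "Women of childbearing potential must utilize a highly effective method of contraception". The same sentence requires a negative pregnancy test within 24 hours before each administration.

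Section 4.1 says what decides eligibility: "All inclusion and exclusion criteria must be met for eligibility".

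Pregnancy prevention also appears in section 4.3.2 ("Counseling related to potential risks of the study product, pregnancy prevention, and HIV risk-reduction will be performed") and in the Appendix I schedules ("Complete a Pregnancy Prevention Form when pregnancy test is given"; "Pregnancy Prevention Counseling when pregnancy test given").

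**The concern.** Two current sections state the contraception rule differently, and the weaker wording is in the list that staff check when enrolling. A clinician working from section 4.1 alone could admit a woman who is out of line with 4.2.1 from Day 0. Section 5.5.3 counts any departure from the approved protocol as a deviation, so relying on the eligibility list could itself produce one.

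The rule matters because this is a first-in-human trial with unknown fetal effects. A pregnancy also stops research sampling and any remaining doses (4.2.1). With groups of 3 or 5, one such subject is 1/3 = 33% or 1/5 = 20% of a group.

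The missing qualifier matters in the other direction. The trial enrolls to age 60, and criterion 17 taken literally asks for birth control from women who cannot conceive.

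**Working it through.** The point rests on no sample size, rate or error probability, and the plan gives no figure to reproduce. The check is a comparison of the places that bear on contraception or eligibility on grounds of pregnancy.

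| Place | Contraception standard | Who | Period |
|---|---|---|---|
| 4.1.1, criterion 17 | effective | women, no qualifier | 21 days before enrollment to end of participation |
| 4.1.1, criterion 18 | none (negative pregnancy test) | women of reproductive potential | day of enrollment |
| 4.1.2, exclusion 1 | none (excludes breast-feeding or planned pregnancy) | women | study participation |
| 4.2.1 | highly effective | women of childbearing potential | none stated |
| 4.3.2 | none (counseling) | not stated | screening |
| Appendix I | none (counseling and form with the pregnancy test) | footnotes to Schedules 1, 2 and 4 name women of reproductive potential for the test | screening to last visit |

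**Step 1: a fertile woman.** Suppose a woman of childbearing potential agrees to a method that is effective but not highly effective. Criterion 17 is met. Criterion 18 is met if her test is negative. Exclusion 1 does not apply if she is neither breast-feeding nor planning a pregnancy. If she meets the other criteria, she passes the list. She does not meet 4.2.1.

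**Step 2: a woman who cannot conceive.** Criterion 18 and 4.2.1 do not reach her. Criterion 17, read literally, does.

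**Step 3: does anything reconcile the two?** Neither term is defined, no acceptable methods are listed, and the terms are nowhere treated as equivalent. The counseling and form entries name no standard.

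**Step 4: are the rules incompatible?** No. A highly effective method is also an effective one, so a fertile woman who meets 4.2.1 for the whole period in criterion 17 meets both.

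**Step 5: is the full rule stated in one place?** No. Criterion 17 has the dates with the weaker standard. Section 4.2.1 has the stronger standard and the narrower population, without dates. The site has to combine them by inference.

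**The case against.** The strongest reply is that nothing is contradictory. Section 4.2.1 is operative and mandatory, section 4.1 does not say that the lists displace it, and a site reading both would apply the stricter rule. That stands. A reader might infer that the protocol permits enrollment on a weaker method; it does not. The gap is that the list used for enrollment omits a requirement set elsewhere.

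Second, screening runs under a separate protocol, and neither the consent nor the Pregnancy Prevention Form is available here. Any of these may already list acceptable methods. This also stands: the practical gap could be nil. It likewise rules out a claim that clinicians at this single site would decide differently about the same woman.

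Third, other safeguards exist: exclusion 1, the negative test before each dose, the scheduled counseling, and the stop to dosing on pregnancy. They limit fetal exposure whatever criterion 17 says. They do not prevent conception after a dose, which is what contraception is for, but they reduce the seriousness.

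Fourth, 4.2.1 may be carried-over text. It calls the antibody a vaccine and contains a failed cross-reference, so criterion 17 might be the intended rule. That is possible, but it does not cancel a mandatory sentence, and lowering the standard is hard to justify while fetal effects are unknown.

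Fifth, the missing qualifier may be drafting shorthand. Schedule 3, footnote 4, drops the same qualifier, and no document shows that a postmenopausal woman would be turned away. This is fair, and it makes that half of the point a matter of clarity.

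**Conclusion.** The inconsistency is real and minor. The eligibility list does not carry the contraception standard of 4.2.1, and criterion 17 is not limited to the women whom 4.2.1 and criterion 18 address. The conclusion rests on the ordinary reading that highly effective is a stricter standard than effective, since the protocol defines neither.

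Its practical size cannot be determined. A reader might try to size it from conception rates under different methods, but the documents give no such rates and no number of women, and assuming rates would build in the contrast. Antibody remaining at later visits does not measure it either, because that describes exposure and not the difference between the two rules. Nothing here shows a known fetal harm, or a problem with when contraception ends. The objectives, dose escalation, sample size and analyses are unaffected.

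**What to change.** Reword criterion 17 so that it (a) applies to women of childbearing potential, (b) requires a highly effective method, and (c) keeps its present start and end dates. For example: *If of childbearing potential, agrees to a highly effective method of birth control over the period now stated in this criterion.* The standard, population and dates are all in the protocol already. Use the same term in the Pregnancy Prevention Form and the consent if they differ. A short list of acceptable methods would settle what the term means.

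The cost is one sentence in 4.1.1, matching words in the two other documents if needed, and the IRB review that any amendment requires. No visit, test or sample is added. The downside is that a few volunteers on less reliable methods must switch before enrollment or are excluded. In return, women who cannot conceive no longer have to agree to birth control.

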4.2. Inclusion of Vulnerable Subjects

4.2.1. Pregnant Women

This is a first-in-human trial in healthy subjects, ≥ 18 years of age. Because the effects of the vaccine on the fetus are not known, pregnant women will not be eligible for the trial. Women of childbearing potential must utilize a highly effective method of contraception and will be required to have a negative urine or serum pregnancy test within 24 hours prior to each product administration.

Pregnancy, if it occurs during study participation, will be recorded in the study database. These participants will not continue to receive any further study product administrations, **Error!**

Reference source not found. research sample collections, or research procedures. Pregnant participants will continue to be followed for clinical safety and to collect the pregnancy outcome. Any follow-up procedures and/or data collected will be for clinical/safety outcome purposes only. Pregnancy will be reported as described in Section 5.6.

4.2.2. Participation of Children

Children are not eligible to participate in this clinical trial because the study agent has not been previously evaluated in adults. If the product is assessed as safe for further study other protocols specifically designed for children may be conducted.

4.2.3. Participation of NIH Employees

NIH employees and members of their immediate families may participate in this protocol. We will follow the Guidelines for the Inclusion of Employees in NIH Research Studies and will give each employee a copy of the “NIH FAQs for NIH Staff Who are Considering Participation in NIH Research” published by Office of Human Research Subjects Protections on Research Involving NIH Staff as Subjects, Policy 404.

For NIH employee subjects, consent will be obtained by an individual who is independent of the employee’s team. If an NIH staff member seeks to enroll in research taking place within their own work unit or conducted by any of their supervisors, the employee will be:

- Informed that neither participation nor refusal to participate as a research subject will have an effect, either beneficial or adverse, on the subject’s employment, training or position at the NIH,

- When possible, consent should be obtained by an individual in a non-supervisory relationship with the subject, and
- When consent is conducted, a third party (e.g. a consent monitor) will be included through the Bioethics Consultation Service or another party independent of the research team or, if a consent monitor is not available, the consent process will be observed by another qualified investigator on the study who is independent of the NIH staff member's work unit and not a supervisor to the NIH staff member. If no such person exists, consent observation may be performed by any qualified investigator on the study. Protocol study staff will be trained on obtaining potentially sensitive and private information from co-workers or subordinates.

4.2.4. Adult Subjects who Lack the Capacity to Consent

Adults who are unable to provide initial informed consent are not eligible to enroll. Also, adults who permanently lose the capacity to provide on-going consent after initial consent and during the study will be discontinued from protocol participation as it is described in [Section 4.5](#)

4.3. Clinical Procedures

Evaluation of study product safety will include laboratory studies, medical history, and physical assessment by clinicians, and subject self-assessment on a diary card for 7 days after product administration. The study schedule is provided in the Schedule of Evaluations, [Appendix I](#). Total blood volume drawn from each subject will comply with the NIH CC Guidelines, which is available on the NIH intranet at the following link:
<http://cc-internal.cc.nih.gov/policies/PDF/M95-9.pdf>. In response to the coronavirus disease 2019 (COVID-19) pandemic and changing information related to testing, all NIH CC epidemiologic and testing guidelines will be followed during study conduct.

The study will be conducted at the Vaccine Evaluation Clinic (VEC) located at the NIH CC. All nursing staff in the VEC are assessed annually for nursing competency including medication administration, peripheral vascular access device care and maintenance, and clinical emergency response. The VEC Clinic is equipped with basic cardiac life support equipment and emergency medications. An advanced clinician (nurse practitioner, physician assistant or physician) is available in the clinic during administration of all investigational study products and throughout the post-administration monitoring period.

4.3.1. Recruitment and Retention Strategies

Study enrollments will be conducted at the NIH Clinical Center. Study subjects will be recruited through the VRC's screening protocol, VRC 500 (NCT 01375530). The on-site and off-site Institutional Review Board (IRB)-approved advertising will be implemented.

Per recruitment plan described in the VRC 500 protocol, efforts will be made to include women and minorities in proportions similar to that of the community from which they are recruited. The recruitment team utilizes a variety of mechanisms to recruit participants including flyer distribution within and outside of the NIH, social media, community tabling events, print and radio ads, listserv emails, posting information on the NIAID/ VRC website, and ResearchMatch.org to effectively recruit potential volunteers.

